4.2 Study design

The study is prospective observational, monocentric

4.3 Measures taken to minimise systematic errors

4.4 Treatment under study (if applicable)

4.5 Expected duration of the subject's participation

12 months

4.6 Rules for interruption (if applicable)

Protocol number

NCT03521193

4.7 Procedures for checking the reliability of the experimental product (if applicable)

4.8 Preservation of randomization codes and procedures for decoding (if applicable)

4.9 Evaluation parameters

The data will be stored on electronic support. All the data reported in the data collection sheet have been obtained from the original documents and agree with the latter. The list of the individual data collected is shown in the "data collection sheet", attached to this document. (excel file)

5. Selection and withdrawal of patients

5.0 Characteristics of the population

The study population includes patients with patent foramen ovale and previous neurological event (TIA or stroke) with clinical indication to the percutaneous correction of the defect according to guidelines or in a previous TIA/stroke absence when addressed to the pfo treatment for migraine non responsive to specific therapy, as per the evaluation of the neurologist specialist. Similar evaluations are not currently available in the literature able to identify patients who, not responsive to specific drug therapy, as prescribed by the neurologist specialist, and carriers of PFO, can be directed to the percutaneous correction of the defect with indication at the moment "off-label" with respect to what is codified by the international guidelines (ESC and AHA / ACC) but potentially effective in the control of symptomatology. The advantage of PFO correction observed so far only in patients undergoing PFO correction as a result of cerebral ischemic events, could translate into migraine workers in a reduction in costs borne by the National Health System in the number of neurological medical examinations, pharmacological prescriptions and missed working days.

5.1 Inclusion criteria

Patients aged > 18 years will need to meet 2 or more criteria:

1. previous Stroke o TIA
2. Positive MRI for ischemic outcomes –
3. presence of PFO with dx-sin shunt in basal conditions > 10 MES and during Valsalva > 20 MES
4. SIA aneurysm or residual Chiari network/Eustachian valve
5. Positive Thrombophilic screening (MTHFR/prot C/Prot S)
6. ability to sign informed consent for participation in the study and adhere to the planned clinical follow-ups

5.2 Exclusion criteria

1. Patients aged > 70 years
2. Presence of paroxysmal atrial fibrillation
3. TSA vasculopathy
4. LV Systolic function < 30%
5. Moderate/severe mitral valve failure

Protocol number

NCT03521193

6. Allergy or intolerance to antiplatelet therapy
7. Allergy to nickel
8. Severe renal failure (GFR < 30 ml/min)

5.3 Criteria for withdrawal

5.4 Informed consent

It is the responsibility of the researcher to obtain written informed consent from the participants before inclusion in the study, after a full explanation of the nature, objectives and risks inherent in participation in the study. The methods of processing personal data and clinical information obtained will also be explained to each participant; the participants in the study will sign the consent to the processing of personal data. It will also be emphasized that participation in the study is voluntary and it will be possible to interrupt it at any time or request at any time the elimination of any biological information or material obtained for research purposes.

6 Treatment of patients

1. 6.1 Treatment/Procedures and evaluations planned during the study

The study, which will take place at the [REDACTED], will be divided into two phases, described below.

Step 1: Screening of symptomatic PFO patients for migraine with aura initiated percutaneous PFO correction and clinical follow-up.

Estimated time: 24 months

This phase of the study aims to test the hypothesis that the population of subjects with PFO and indication to percutaneous correction of the defect, when symptomatic for migraine with or without aura, can be characterized as responders or non-responders with regression of the migraine symptomatology / aura.

The identification of symptomatic patients for migraine, after preliminary neurological evaluation, will be accompanied by a classification of migraine according to the severity scale of migraine sec. Anzola (Table 1). This evaluation will be repeated after PFO correction and outpatient clinical follow-up at a distance of 6 and 12 months, together with the execution of color-Doppler TT echocardiogram. This last examination will characterize the correct positioning of the PFO occlusive device and the presence/absence of residual inter-atrial shunt dx-sin.

TABLE 1. Migraine Severity Score

Intensity
0=No pain
1=Moderate (does not interfere with the performance of daily activities)
2=Severe (interferes with the performance of daily activities)
3=Inbearable (requires enticing)
Duration

Protocol number

NCT03521193

0=No pain

1=<6 hours

2=6–12 hours

3=>12 hours

Frequency

0=No pain

1=1–4/month

2=5–9/month

3=>10/month

Aura

0=No aura

OCCLUDER DEVICE FOR PFO

1. The Occlutech Figulla device consists of a single layer of nitinol meshes that conform to give rise to 2 flexible discs (the left disc with diameter smaller than 2 mm) with a perno only on the right side. The discs are connected to each other thanks to a flexible and compressible central portion the size of 3 mm. The left disc is a flat monolayer covered with an ultra-thin piece of polyethylene terephthalate. The size of the Figulla device is determined by the diameter of the two discs in the following configurations: 16/18, 23/25, 27/30 and 31/35 mm.

PFO CORRECTION PROCEDURE

1. Pfo correction will be performed percutaneously under local anesthesia with bilateral femoral venous puncture by placement of introducer 6F in the right femoral vein and 8F in the left femoral vein. The 8F introducer will be replaced at site with the placement of 45-cm, 8.5 F Slow-curve introducer for the advancement of the intracardiac ultrasonographic catheter (Ultra ICE™, Boston Scientific, Marlborough, MA, USA). This probe, with the advantage of avoiding the intubation of the patient, will allow to characterize the anatomy of the SIA and allow the measurements of the oval fossa and the presence / absence of aneurysm of the SIA for the most appropriate choice of the occlusive device suitable for size and to monitor the positioning and implantation of the occlusive device. A 0.035" guide wire with J tip will be positioned through the interatrial septa into the superior pulmonary vein. In all cases an occlusive device of adequate size will be loaded inside a moon cannula of the size between 7-10 F and advanced pushing the release cable to the end of the introducer positioned in the left atrium. Under fluoroscopic and intracardiac ultrasound guidance, the left disc of the device will be implanted and approached against the left side of the SIA. With a slight voltage maneuver on the release cable, the cannula will be retracted allowing the right disc to be implanted. The intracardiac ultrasound evaluation will allow to evaluate the correct positioning of the device and the absence of images related to coronary obstruction and / or pulmonary venous return or compression of the aortic root and atrioventricular valves. At this point the device will be permanently released.

INTRA E POST-PROCEDURE THERAPY

Protocol number

NCT03521193

Patients will receive 70 IU/Kg of heparin at the beginning of the procedure in order to maintain the ACT (activated platelet aggregation time) value > 200 seconds. Aspirin 100 mg will already be therapy in place for more than 7 days and continued for at least 6 months after the correction of PFO while Clopidogrel 75 mg will be administered immediately after the procedure and continued for 2-3 months in patients treated with implantation of devices > 25 mm diameter. Antibiotic prophylaxis will be started before the procedure and continued for the next 5 days.

FOLLOW-UP

The clinical and diagnostic follow-up with cardiological examination, color-Doppler echocardiogram at 6 and 12 months and compilation of the Migraine severity score scale (Table 1), will allow to evaluate any residual shunts post correction of PFO and the beneficial effects on the control of migraine symptoms by reassessment of the Anzola score.

Phase 2: Analysis of platelet reactivity and levels of inflammatory cytokines, PGE1, PGE2 and serotonin in migraine patients with PFO.

Estimated time: 24 months

This phase of the study aims to investigate whether the beneficial effect of PFO correction on migraine is secondary to a barrier mechanism to platelet microembolization and that this response may correlate with the parameters of platelet function and activation. For this purpose, the study of platelet function will be carried out before the correction of PFO and 180 days after surgery.

For the evaluation of the parameters of platelet function from each patient, a blood sample will be taken in the absence of stasis, in order to avoid platelet activation, from the antecubital vein of the forearm by means of a G19 needle. Before proceeding with the separation of the platelets, a quantitative hematology analysis will be performed with leukocyte formula and platelet count by means of Sysmex XS 1000 automatic blood count.

Cytofluorimetry studies will allow to characterize the state of platelet activation in terms of protein expression both on the cell surface and inside the cell. In particular, the expression of P-selectin, activated GpIIb/IIIa, Tissue Factor and Phosphatidylserine will be evaluated through the use of specific monoclonal antibodies. These analyses will be performed both in basal conditions and after *in vitro* activation with agonists such as ADP, thrombin and epinephrine. The same conditions will also be used for the evaluation of the presence of mixed aggregates, platelet-leukocytes, sensitive index of platelet activation.

PRP (Platelet-Rich Plasma), separated from the blood by centrifugation, will be used to perform platelet aggregation studies in response to different agonists such as ADP, collagen, thrombin, epinephrine and arachidonic acid.

The characterization of the circulating microvesicles will be performed on samples of Platelet-Free Plasma (PLP), by means of a multiparametric analysis performed using the new generation cytofluorimeters. In particular, not only the total number of microvesicles present in the sample will be considered, but a detailed phenotyping will be performed that will give information on the

Protocol number

NCT03521193

cellular derivation of the microvesicles, considering in particular those of platelet, leukocyte and endothelial origin.

Serum TXB₂ levels and urinary excretion of 11-dehydro-TXB₂ will be evaluated by mass spectrometry.

The levels of the inflammatory cytokines IL-1, IL-6, TNF α will be measured on plasma samples with enzyme immunoassay, while the levels of PGE₁, PGE₂ and serotonin will be dosed by HPLC method.

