In women and patients with stable coronary artery disease, in antiplatelet therapy with aspirin, high platelet reactivity (HAPR) or resistance to aspirin has been described and is associated with adverse clinical outcomes. A study conducted by Jesurum et al, suggested that subjects with migraine have a higher prevalence of HAPR than healthy subjects or patients with stable coronary artery disease being treated with aspirin 325 mg. However, the clinical implications of HAPR in subjects with migraine and PFO require further investigation of analysis for the high risk of cerebral stroke and myocardial infarction and the need to prescribe early prevention therapy.

A PFO with dx-sin shunt should require a neurological substrate susceptible and vulnerable to some substance that by-passes the pulmonary circle and induces headache. The endothelium of the

Protocol number

NCT03521193

pulmonary circle has significant metabolic activity. The lung in fact metabolizes, activates or inactivates many compounds including vasoactive amines and other humoral substances²⁵. Prostaglandins E1, E2 and F2 are completely removed from the bloodstream; serotonin is removed between 85% and 95%; 70% of angiotensin I is converted to angiotensin II, and 80% of bradykinin is inactivated²⁶. It is not known whether these substances may increase the susceptibility of the brain to stimulate environmental or intrinsic triggers capable of triggering migraine

Objectives and aims of the study

The aim of the study is to verify whether vasoactive/inflammatory substances together with increased platelet reactivity may play a key role in the onset of migraine and in its maintenance even after correction of PFO. The morphological and anatomical characteristics of the oval fossa will also be analyzed in order to identify elements that can correlate with increased platelet reactivity and predict a clear benefit in the control of migraine symptoms after correction of PFO. The analysis will also be extended to the evaluation of differences between female and male sex.

4. Study design

1. 4.1 Primary and secondary outcomes

Primary outcomes:

Evaluation of the % regression of migraine episodes with aura in relation to platelet reactivity in migraine patients, with and without aura, carriers of PFO, together with the dosage of PGE1, PGE2, serotonin and cytokines in order to identify potential predictive markers of beneficial effect of PFO correction on migraine symptoms.

Secondary outcomes

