8.4 Type and duration of subjects following adverse events

9. statistical analysis

9.1 statistical analysis

Continuous variables will be summarized using the DS \pm mean. Categorical variables are represented using frequencies and percentages. For the comparison between responders and non-responders, the Student's 2-code t-test or the Wilcoxon test for continuous variables will be used. The Chi-square test or the Fisher test will be used for categorical variables.

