9.2 Calculation of the sample number

The sample size calculation is based on the 1-year primary endpoint. A value for the frequency of reaching the primary endpoint was placed around 60%, in accordance with the data reported in

Protocol number

NCT03521193

literature^{22, 27}. A sample of 92 patients was identified, necessary to obtain a potency of 80% able to detect as significant ($p < 0.01$, considering the Bonferroni correction for multiple tests) a correlation coefficient of 0.35 (adjusted for 4 confounding variables) between the variation of the migraine score sec. Anzola and any of the 5 factors (platelet reactivity, PGE1, PGE2, cytokines, serotonin) measured at baseline.

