9.3 Significance level to use

Statistical significance will be considered that obtained with a p value of 0.05.

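### Baseline blood sampling is not timed against migraine attacks, and time since the last attack is not recorded in the protocol text, so marker associations may be diluted and partly confounded with attack frequency

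*Combined protocol and SAP*

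**What the plan says.** Section 6.1, Phase 2, sets two times for the platelet-function study: one ahead of closure and one at 180 days. It controls how the sample is drawn: "a blood sample will be taken in the absence of stasis, in order to avoid platelet activation, from the antecubital vein", with a specified needle. The assay description that follows covers platelet markers, aggregation, microvesicles, thromboxane, cytokines, PGE1, PGE2 and serotonin, and adds no timing rule. Section 9.2 says only that the five factors are measured at baseline. The 180-day repeat is stated for platelet function alone.

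The aims section proposes that "vasoactive/inflammatory substances together with increased platelet reactivity may play a key role in the onset of migraine".

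In section 9.2, "A sample of 92 patients was identified", "necessary to obtain a potency of 80"%, to detect "a correlation coefficient of 0.35 (adjusted for 4 confounding variables") between each factor and the change in Anzola score, at p < 0.01 "considering the Bonferroni correction for multiple tests". The four confounders are not named. Table 1 shows that attack frequency is one item of the Anzola score. Section 9.1 lists only unadjusted comparisons of responders with non-responders. Sections 6.2 (permitted treatments) and 9.5 (missing or spurious data) are headings without text.

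**The concern.** The plan accepts that the conditions of the draw affect these assays, since it controls stasis to prevent platelet activation. It leaves open the condition closest to its own hypothesis: whether the patient is in or near an attack, or has just taken a drug for one.

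Two consequences follow if markers shift around attacks. First, each patient has one baseline value, and part of its variation would reflect the day of the draw rather than a lasting characteristic of the patient. That weakens any true correlation with outcome. Second, patients with more attacks are more likely to be sampled near one, so the marker carries some information about attack frequency, which is also part of the outcome score. Timing that was never recorded cannot be reliably reconstructed at analysis.

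**Working it through.** **1. The plan's own figure.** Inputs from section 9.2: r = 0.35, alpha 0.01 (0.05/5), power 80%, 4 covariates. Two-sided testing is assumed for the correlation; section 9.1 states it for the t-test. A noncentral F test of one predictor with 4 covariates (f² = r²/(1 − r²), df = n − 6, λ = (df + 2)f²) gives exactly 92, with power 0.805. Fisher z with k covariates gives

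n = ((2.576 + 0.842)/atanh 0.35)² + 3 + k = 87.45 + 3 + k,

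that is, 91 for k = 0 and 95 for k = 4. The stated 92 is reproduced. Below I use Fisher z with k = 4, for which power at 92 is Φ(0.3654 × √85 − 2.576) = 0.786.

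**2. Chance of a sample near an attack.** Assume a draw on a random day and a 24-hour window around each attack. The probability is attacks per month × 24/720:

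| Attacks/month | Probability |
|---|---|
| 1 | 3% |
| 4 | 13% |
| 9 | 30% |
| 12 | 40% |

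With windows of 12 to 48 hours the range is about 2% (1 attack, 12 h) to 80% (12 attacks, 48 h).

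**3. Dilution.** If attack phase explains a share s of marker variance and is otherwise unrelated to outcome, the observed correlation is 0.35 × √(1 − s). Power is Φ(atanh r × √85 − 2.576). The shares are assumptions; the documents give none.

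| s | r | Power at N = 92 | N for 80% power |
|---|---|---|---|
| 0 | 0.350 | 79% | 95 |
| 10% | 0.332 | 73% | 106 |
| 20% | 0.313 | 66% | 119 |
| 30% | 0.293 | 58% | 136 |

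What these shares imply: from s/(1 − s) = p(1 − p) × shift², with p = 0.13 (4 attacks/month, 24 h), they need marker shifts of about 1.0, 1.5 and 1.9 SD near an attack.

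**4. Simulation as a second route.** Assumptions: 92 patients, attack days uniform on 1 to 14 per month, 60% responders, and a marker shift of 0.5, 1 or 2 SD within one day either side of an attack.

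- Dilution: r falls to 0.340, 0.313 and 0.247, and power to 75%, 66% and 40%.
- Correlation of marker with frequency: 0.11, 0.21 and 0.33. Across windows from the attack day alone to two days either side, it runs from 0.06 to 0.35.
- With no true marker effect, the spurious marker–outcome correlation is 0.01 to 0.07, and rejection at nominal 0.01 is 0.011 to 0.026 over all windows.
- Adjusting for baseline frequency brings rejection back to 0.006 to 0.012, which is nominal within simulation error.
- With zero shift, there is no dilution and no induced correlation.

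**5. Dependence on alpha.** Section 9.3 reads "Statistical significance will be considered that obtained with a p value of 0.05", which does not match section 9.2. At two-sided 0.05, even s = 30% gives Φ(0.3017 × √85 − 1.960) = Φ(0.82), about 79%. The power loss in step 3 therefore applies to the corrected level on which the sample size was built.

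**The case against.** A reader might infer that the baseline marker becomes a proxy for attack frequency and will yield a false predictor. The documents do not support that. They give no marker change around attacks, and the rationale also describes a standing mechanism (platelet activation in the tunnel, substances bypassing the lung) that fits a level raised between attacks as well. Even a 2 SD shift gives a marker–frequency correlation of at most about 0.35, or 12% of marker variance, and a small rise in false positives. Baseline frequency may already be one of the four unnamed confounders.

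A reader might also infer that the before/after fall of every marker is biased by fewer attack-day samples at 180 days. The repeat is stated for platelet function only, and section 9 specifies no before/after marker test.

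The variance shares in the dilution table are assumed, as is a random sampling day. Draws follow planned care, and the inclusion criteria set no migraine frequency, so the share of frequent attackers is unknown. The data collection sheet cited in section 4.9 is a separate file, was not available, and might record the last attack.

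All of this stands and limits the claim. It does not supply a timing rule. Adjusting for frequency would remove the confounding but would not recover power lost to day-to-day attack-phase noise.

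**Conclusion.** The gap is real and its consequence is conditional. The protocol text times sampling only by closure and records nothing about attack proximity. If markers move around attacks, the baseline predictor may be diluted and partly confounded with an item of the outcome score. Dilution matters more: power at N = 92 and p < 0.01 falls from about 79% to between 73% and 58% for assumed variance shares of 10% to 30%, and is unchanged if markers do not move. No dropout allowance is stated that could absorb such a loss. The false-positive effect is small and disappears on adjustment for baseline frequency. This is a worthwhile, cheap improvement; it does not show that the design is invalid.

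**What to change.** - At each draw (baseline for all markers, 180 days for platelet function), record hours since the last migraine attack and since the last acute migraine drug. First check whether the data collection sheet already does so.
- Where scheduling allows, and without delaying closure or changing any treatment, draw on an attack-free day with a minimum interval fixed in advance.
- Keep and flag samples that miss the interval.
- Name baseline attack frequency among the four adjustment covariates of section 9.2.
- Keep all samples in the main analysis and adjust for the flag. Report the analysis without flagged samples as a sensitivity analysis only, because exclusion selects against frequent attackers.

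The cost is a short timing question at each draw, some rescheduling, and one more covariate (one more patient by the Fisher z formula). Flagged samples could be numerous in patients with very frequent attacks. At 12 attacks a month, with attacks assumed to follow a Poisson process, the chance of no attack in the previous 48 or 72 hours is exp(−12 × 48/720) = 45% or exp(−12 × 72/720) = 30%. Those intervals are for illustration; the investigators should choose the interval.

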6.2 Treatments allowed and not before/during the trial

6.3 Procedures to monitor patient compliance (if applicable)

7. Efficacy/endpoint evaluation

7.1 Specifying Effectiveness/Endpoint Parameters

Primary endpoints:

Secondary endpoints

7.2 Methods and times for the assessment, recording and analysis of effectiveness parameters

8. Safety/tolerability assessment

